16.2 Contrast Administration Guidelines for NH002

NH002 Administration: for further details, see also the current version of the NH002 Investigator's Brochure.

1. Obtain IV access or evaluate for an existing IV line. (May be given through a peripherally inserted central catheter [PICC] or central line if necessary.)
2. NH002 is to [REDACTED] using the TRANSMIX™ vial [REDACTED]
3. NH002 is to be activated for [REDACTED] TRANSMIX activation cycle, and will appear as a milky-white suspension. Do not use this drug unless it has completed a full [REDACTED] activation cycle in the TRANSMIX™. Do not reactivate the vial if TRANSMIX™ did not complete a full [REDACTED]; the product should not be used. Do not reactivate a successfully activated NH002 vial.
4. Invert the vial and withdraw the activated milky white suspension using an 18- to 20-gauge syringe needle. Withdraw the material from the middle of the liquid in the inverted vial. Do not inject air into the vial. Use the product immediately after its withdrawal from the vial; do not allow the product to stand in the syringe.
5. Administer activated NH002 into the IV port closest to the IV site.
6. Injections are to be administered slowly, over 30 to 60 seconds, followed by a 10 mL saline flush over 10 seconds.

NOTE: Contact the sponsor or clinical research associate for further instructions. Do not discard the vial(s).

2		
1. Remove Section 5.5.1 LVEBD Score for Subjects with Suboptimal LVEBD (LVEBD Score < 14 and at Least 4 Segments with a Delineation Rating of +1 or +2) at Baseline.2. Add Section 7.2.2 External Data Transfer.	
1. According to the protocol, the Suboptimal LVEBD at Baseline is as defined by 2 or more contiguous segments of 6 segments that cannot be visualized reliably in either the apical 4- and/or the 2-chamber view, as assessed by the blinded central reader(s).2. The external data is transferred by [REDACTED] Inc. and Trust Bio-sonics, Inc.

1. Introduction

This Statistical Analysis Plan (SAP) contains a more technical and detailed elaboration of the principal features of the analysis described in the protocol, and includes detailed procedures for executing the statistical analysis of the primary and secondary variables and other data. The SAP is finalized and signed prior to hard lock of the database.

1.1. Flow Chart and Visit Schedule

	Screening ≤ 28 Days before Day 1, unless otherwise specified	Dosing Period								Safety Follow-up	
		Day 1								Day 4	Day 7
		Before dosing (t)	-5 min	t=0	+10 min	+30 min	+60 min	+120 min	+240 min	72 hours after EOT	7 days after EOT
Time window	N/A	N/A	N/A	(+2 min ²)	(+2 min ²)	+5 min	+5 min	+5 min	+5 min	+3 days	+3 days
Informed consent	X										
Eligibility review	X	X									
Demography	X										
Medical history (signs/symptoms)	X	X									
Vital signs ¹	X	X		X-----X		X	X	X			
Height (cm)	X										
Weight (kg)	X	X									
Standard 12-lead ECG	X	X			X ²		X	X			
Modified 12-lead ECG				X ³ -----X ³							
PE	X ⁴	X ⁵									
Contrast agent IV bolus injection				X							
Imaging				X ⁶ -----X ⁶							
Pregnancy test(s) (WoCBP only)	X ⁷	X ⁷									
CBC (with differential) ⁸		X					X	X	X		
TT and aPTT		X					X	X	X		
Metabolic panel ⁹		X					X	X	X		
Cardiac troponin I ¹⁰		X							X		
Pulse oximetry: SpO ₂		X	X-----X		X	X	X				
Telephone call										X	X
Adverse events			X-----X							X	X
Concomitant medications	X	X-----X								X	X

NOTES:

1 Vital signs to include body temperature, HR, RR, and BP.

2 The time window of +2 minutes only applies to the standard 12-lead ECG assessment(s) scheduled or conditionally triggered within 10 minutes after dosing.

3 If any clinically significant ECG changes indicative of arrhythmia or S-T segment change are identified after dosing from the modified 12-lead ECG monitoring, a standard 12-lead ECG examination will be performed subsequently (after the first ECG change occurs). The imaging will be temporarily stopped for the conditionally triggered standard 12-lead ECG examination. All the identified ECG changes from the modified 12-lead ECG monitoring will be recorded in a timely manner. The results of the modified 12-lead ECG will also be included into the subject's study file as reference. Further, safety assessments will be based on the results of the standard 12-lead ECG. If such ECG changes occur during both the modified 12-lead ECG monitoring and the subsequent confirmatory standard 12-

lead ECG examination in 2 or more subjects during the study, the protocol will be revised to require a standard 12-lead ECG examination be performed for all subsequent subjects at an earlier post-injection time point when these early ECG changes may potentially occur.

4 Complete PE at screening to include assessments of general appearance, skin (turgor, pallor, cyanosis, erythema, lesions), head (eyes, ear, nose, and throat), neck, lungs and heart (observation, palpation, percussion, auscultation), abdomen, back, lymph nodes, and extremities and a neurological exam.

5 Focused PE (all PEs after screening) to include cardiopulmonary (observation, palpation, percussion, auscultation) and skin (turgor, pallor, cyanosis, erythema, lesions) assessments.

6 B-mode echocardiography and contrast-specific ultrasonography will be employed for all pre-injection and unenhanced images, while post-injection images will be acquired through contrast-specific ultrasonography only.

7 Urine or serum (β -HCG) pregnancy test is required for WoCBP at screening; it is *not* required for postmenopausal or surgically-sterilized women. For WoCBP, urine *and* serum pregnancy tests are *both* required before dosing on Day 1.

8 CBC to include HCT, Hgb, WBC with differential, ANC, and PLT.

9 Metabolic panel to include sodium, potassium, chloride, calcium, magnesium, phosphorus, glucose, BUN, creatinine, total protein, albumin, ALP, ALT, AST, total bilirubin, and bicarbonate.

10 Cardiac troponin I levels should be measured before dosing and once again at 4 hours after dosing in all subjects.

1.2. Study Design

This is a phase 1, multicenter, open-label clinical study to evaluate the safety and tolerability of 3 ascending doses of NH002. Up to 36 eligible subjects will be enrolled with sequential allocation to 1 of 3 cohorts with the following intravenous (IV) doses of NH002: 2.5 μ l/kg, 5.0 μ l/kg, or 10.0 μ l/kg. Each patient will undergo an unenhanced ultrasound examination and a NH002 contrast-enhanced examination on the same day at Day 1. Subjects will remain at the clinical site for 240 minutes of observation after NH002 administration.

All AEs will be evaluated during the successive groups of subjects, per dose level. In general, enrollment will be halted and safety data reviewed for termination or continuation with the occurrence of any serious adverse event (SAE) considered at least possibly related to study agent administration (in any 1 subject) or the occurrence of clinically significant toxicity listed in the study protocol in 30% of subjects (within any 1 of the 3 dose levels). See Section 7.5.1.2 in the study protocol for details on stopping criteria for dosing for this trial.

There will be a screening period (28 days before NH002 administration), a dosing period (during Day 1) which will include a single dose administration of NH002, and a 7-day follow-up period for each cohort. Continuous echocardiographic imaging will be performed at specified time points before, during, and after dose administration. The contrast agent will be prepared and administered by designated pharmacy technician(s), study nurse(s), sonographer, or radiologist. Subjects will be observed at a clinical site for at least 240 minutes (i.e., 4 hours) and evaluated for AEs. Subjects will be contacted by phone after the end of treatment at 72 hours (i.e., Day 4 [+3]) and at Day 7 (+3), for a follow-up safety assessment. Any drug-related AE or SAE will be followed until resolution.

High ultrasound mechanical index (MI) values may cause microsphere cavitation or rupture and lead to ventricular arrhythmias. Additionally, end-systolic triggering with high MIs has been reported to cause ventricular arrhythmias. The safety of NH002 at MIs greater than 0.8 will not be evaluated.

1.3. Randomization

This is a phase 1 dose ascending study without the use of an active control as well as a placebo control. No dose or treatment randomization is applicable.

1.4. Objectives and Endpoints

Objectives	Endpoints
Primary	
To evaluate the safety and tolerability of 3 different ascending doses of NH002. 
Treatment Emergent Adverse event (TEAE) reporting and changes in physical examination findings, vital signs (VS), clinical laboratory evaluations, other laboratory evaluations, oxygen saturation, and electrocardiograms (ECGs).
Secondary	
To evaluate the preliminary diagnostic efficacy of NH002 as a contrast agent in echocardiography. 
The percentage of subjects with moderate or complete LVO, defined by an LVO grade of 2 (moderate) or 3 (complete), as assessed by the blinded central reader(s);The percentage of subjects with complete LVO, defined by an LVO grade of 3 (complete), as assessed by the blinded central reader(s);The change from baseline on the left ventricular endocardial border delineation (LVEBD) score, defined using a standard 12-segment model, as assessed by the blinded central reader(s). The LV endocardium of the 4- or 2-chamber apical views are divided into 6 segments, with 2 basal, mid- and apical segments in each view. For each segment, LVEBD is graded as follows: 0 = inadequate border (border not visible); 1 = sufficient (border barely visible); 2 = good (border clearly visible). A total delineation score (0-24) is obtained by adding the scores from the 6 individual segments in each of the 2 views;The changes from baseline on LVEBD score of subjects with suboptimal LVEBD at baseline, as defined by 2 or more contiguous segments of 6 segments that cannot be visualized reliably in either the apical 4- and/or the 2-chamber view, as assessed by the blinded central reader(s);

	
• The duration of clinically useful contrast calculated by measuring the time between the disappearance of shadowing effect (useful effect starts) and the time when moderate or full LV enhancement and contrast enhancement are no longer adequate (useful effect ends), as assessed by the blinded central reader(s).
--	--

2. Statistical Hypotheses

Not applicable.

3. Sample Size Determination

It is anticipated that 36 subjects will be enrolled (with up to 12 subjects per NH002 dose). Each subject will receive 1 dose of NH002. If a subject is withdrawn from the study, the subject may be replaced with another subject assigned to the same dose, except for those who are discontinued due to AEs, as necessary. Further subjects may be enrolled at a given dose level if additional data are necessary to establish safety and tolerability prior to dose escalation. As this is a dose-finding study, a formal sample size calculation was not required

4. Populations for Analysis

In accordance with ICH recommendations in guidelines E3 and E9, the following analysis sets will be used for the analyses.

The Full Analysis Set and Per Protocol Set will be used for summaries of demographic and baseline characteristics and efficacy variables. The Safety Set will be used for summaries of demographic and baseline characteristics and all safety variables.

4.1. Full Analysis Set (FAS)

The Full Analysis Set (FAS) will consist of all enrolled subjects who have completed all study evaluation periods, and received 1 dose injection of NH002.

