7.1.1 Imaging Guidelines

In accordance with protocol guidelines for imaging, each study center will follow standard practice for (transthoracic) echocardiographic imaging and subject preparation. This includes subject positioning and comfort measures, pre- and post-dosing.

Refer to [Image Evaluation Guidelines](#) for details.

The 2008 American Society of Echocardiography consensus statement on contrast agents in echocardiography advocates a team approach for the successful introduction and implementation of contrast protocols into an echocardiography laboratory.⁴ The team would primarily consist of the sonographer, physician echocardiographer, and where available, nursing staff who are competent and certified in obtaining IV access and administration of IV agents.

It is recommended that the sonographers be appropriately qualified and credentialed in echocardiography and the responsible investigators be independent and competent echocardiographers with skills in basic and advanced life support.

Each subject will undergo an unenhanced ultrasound examination. After unenhanced imaging, subjects will then receive 1 dose of NH002 at the assigned cohort dose level. Before contrast administration, the instrument settings on the ultrasound imaging system, including gain, MI,

[figure not shown]
focal depth, time gain compensation, and dynamic range will be optimized for each subject and kept constant during the imaging.

For each dose, two-dimensional transthoracic echocardiography will be performed using both B-mode ultrasonography and contrast-specific ultrasonography before agent administration and using only contrast-specific ultrasonography after agent administration. The pre-injection imaging will be performed once in both apical 4- and 2-chamber views, first using B-mode ultrasonography and then contrast-specific ultrasonography. Switch between both apical views or imaging modes will be performed in 30-second intervals. Upon NH002 administration, the post-injection imaging will be subsequently performed in both apical 4- and 2-chamber views using only contrast-specific ultrasonography. During this period, alternation of both apical views will be performed in 30-seconds until 10 minutes after NH002 administration. In both imaging sessions, the 4-chamber view will be performed first.

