4.2. Per Protocol Set (PP)

The Per Protocol Set will be a subset of the Full Analysis Set and will include all subjects who completed all study evaluation periods, received 1 dose injection of NH002 and had no major protocol deviations.

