5.4.1.2. Main analytical approach

- LVO Grade

A pair of apical 4-chamber and 2-chamber view images in each of the pre-injection and post-injection imaging sessions will be subjected to LVO grade assessment by central reading.

The highest LVO Grade among the pair of apical 4-chamber and 2-chamber view images of pre-injection and post-injection will be summarized and presented by each dose group and overall. When the LVO grades of both apical 4-chamber and 2-chamber view images are the same, the LVO grade of the apical 4-chamber view image will be used.

The following descriptive statistics will be summarized and presented:

- Number and percentage of subjects in each LVO Grade.
- Number and percentage of subjects with moderate or complete LVO.

In addition, the bar chart for Cumulative Percent of LVO Grade will be presented by pre-dose and post-dose groups in each cohort and overall.

Two LVO grades obtained for each session along with the corresponding times of images used will be listed.

- Table 12.1.1: Summary of LVO Grade, Full Analysis Set
- Figure 12.1.2: Cumulative Percent of LVO Grade, Full Analysis Set
- Table 12.2.1: Summary of LVO Grade, Per Protocol Set
- Figure 12.2.2: Cumulative Percent of LVO Grade, Per Protocol Set
- Listing 06.1: Image Evaluation - LVO Grade, Safety Set

- LVEBD Score

The descriptive statistics (n, mean, standard deviation, median, minimum, maximum, and 95% CI) of LVEBD score for pre-injection, post-injection and the change from baseline will be summarized and presented by each dose group and overall. LVEBD scores for subjects with suboptimal LVEBD at baseline (as defined by 2 or more contiguous segments of 6 segments that cannot be visualized reliably in either the apical 4- and/or the 2-chamber view) will also be summarized.

Moreover, the boxplots of the LVEBD score for pre-injection, post-injection and the change of LVEBD score will be presented by each cohort and overall.

Likewise, for subjects with suboptimal LVEBD at Baseline (as defined by 2 or more contiguous segments of 6 segments that cannot be visualized reliably in either the apical 4- and/or the 2-chamber view), the boxplots of the LVEBD Score for pre-injection, post-injection and the change of LVEBD score will be presented by each cohort and overall.

- Table 13.1.1.1: Summary of LVEBD Score, Full Analysis Set
- Figure 13.1.1.2: LVEBD Score, Full Analysis Set
- Figure 13.1.1.3: Change of LVEBD Score, Full Analysis Set

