- Table 14.1.1: Summary of Duration of Clinically Useful Contrast Enhancement, Full Analysis Set
- Figure 14.1.2: Duration of Clinically Useful Contrast Enhancement, Full Analysis Set
- Table 14.2.1: Summary of Duration of Clinically Useful Contrast Enhancement, Per Protocol Set
- Figure 14.2.2: Duration of Clinically Useful Contrast Enhancement, Per Protocol Set
- Listing 06.3: Image Evaluation - Duration of Clinically Useful Contrast Enhancement, Safety Set

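### The Full Analysis Set requires study completion, so a dosed subject with complete image reads who later drops out is left out of every efficacy table and figure

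*SAP*

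**What the plan says.** SAP 4.1 defines the FAS as "all enrolled subjects who have completed all study evaluation periods, and received 1 dose injection of NH002". Protocol 10.2 uses the same words. SAP 4.2 adds that "The Per Protocol Set will be a subset of the Full Analysis Set" and repeats the completion condition. The Safety Set (SAP 4.3) requires only that NH002 was injected.

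SAP section 4 then assigns the sets: "The Full Analysis Set and Per Protocol Set will be used for summaries of demographic and baseline characteristics and efficacy variables". The output lists in SAP 5.4.1.2 follow this. Every efficacy table and figure (series 12, 13 and 14) is labelled FAS or Per Protocol. Only the individual listings are wider: "Listing 06.1: Image Evaluation - LVO Grade, Safety Set", the matching Listing 06.2 for LVEBD, and "Listing 06.3: Image Evaluation - Duration of Clinically Useful Contrast Enhancement, Safety Set".

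On timing, Protocol 7.1.1 has post-injection imaging run so that "alternation of both apical views will be performed in 30-seconds until 10 minutes after NH002 administration". SAP 1.2 describes a screening period, a dosing period on Day 1 and "a 7-day follow-up period for each cohort". Follow-up consists of telephone safety contacts at Day 4 and Day 7 (Protocol 8.3).

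On replacement, SAP section 3 says that "the subject may be replaced with another subject assigned to the same dose, except for those who are discontinued due to AEs". Protocol 7.4.4 is firmer: non-compliant subjects and those who withdraw consent are to be replaced, and those who stop for other reasons such as an AE are not.

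**The concern.** All scheduled efficacy data exist 10 minutes after dosing. Nothing in the later observation or the two calls adds to the LVO grade, the LVEBD score or the duration of useful contrast. Making FAS membership depend on completing those later stages conditions the efficacy summaries on something that happens after the outcome has been recorded, and the documents give no reason for it.

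The plan expects such subjects. Protocol 7.4.4 lists loss to follow-up, subject request and AEs as grounds for withdrawal, and SAP 5.2.1 counts injected subjects who did not complete. An AE excludes nobody by itself, but failing to complete does. Whether an unanswered follow-up call counts as failing to complete is not stated, so that decision could be taken once data are in hand.

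The usual check, comparing FAS with Per Protocol, cannot show the effect because both sets carry the same condition. No efficacy table covers all dosed subjects with reads. The summaries also have a stated use: Protocol 10.6 says dose selection rules will draw on efficacy as well as safety.

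**Working it through.** **Step 1. The plan's own figure.** Three cohorts of 12 give 3 × 12 = 36, as stated in SAP section 3. The plan gives no alpha, power, effect size or dropout rate, so there is no other figure to reproduce.

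**Step 2. Trace one subject through the sets.** Take a subject who is dosed, has complete pre- and post-injection reads, and is lost before the Day 7 call.

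| Set | Condition | Subject included? | Efficacy outputs |
|---|---|---|---|
| Safety Set (SAP 4.3) | injected | yes | Listings 06.1–06.3 only |
| FAS (SAP 4.1) | injected and completed all evaluation periods | no, if follow-up is such a period | FAS tables and figures in series 12–14 |
| Per Protocol (SAP 4.2) | FAS and no major deviation | no | Per Protocol tables and figures in series 12–14 |

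The one interpretive step is whether follow-up is an evaluation period. SAP 1.2 and Protocol 7.1 name screening, dosing and follow-up as the periods, and Protocol 8.3 titles follow-up as one.

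**Step 3. Effect of one exclusion without replacement.** The cohort size of 12 is from the plan; the 10 responders (LVO grade 2 or 3) are an illustration.

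- Share of the cohort removed: 1/12 = 8.3%.
- All dosed and read: 10/12 = 83.3%.
- Reported if the dropped subject is a non-responder: 10/11 = 90.9%.
- Reported if the dropped subject is a responder: 9/11 = 81.8%.

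With two exclusions, the reported figure lies between 8/10 = 80.0% and 10/10 = 100.0%.

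**Step 4. Effect of one exclusion with replacement.** Thirteen are dosed and 12 analysed. A reported 10/12 = 83.3% then stands for:

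- 10/13 = 76.9% of those dosed, if the dropped subject was a non-responder;
- 11/13 = 84.6%, if the dropped subject was a responder.

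Replacement restores the count but not the discarded read.

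**Step 5. How often.** The documents give no non-completion rate, so q is an assumption: 5%, range 3–10%. Subjects are treated as independent.

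| Assumed q | P(at least one of 12) = 1 − (1 − q)^12 | Expected per cohort = 12q |
|---|---|---|
| 0.03 | 0.306 | 0.36 |
| 0.05 | 0.460 | 0.60 |
| 0.10 | 0.718 | 1.20 |

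Across all 36 subjects, 1 − (1 − q)^36 is 0.842 at 5% and 0.977 at 10%.

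**The case against.** The strongest objection is that completion of evaluation periods is undefined, and the exclusion follows only if follow-up is included. The protocol uses the word period loosely: Protocol 7.1.1 applies dosing period to the recording window of about 15 minutes. A Day 1-only reading is possible. This stands as a caveat, but it does not rescue the text. The documents name follow-up as a period, and if the sponsor means something narrower, the definition has to say so.

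Second, the stakes are limited. Efficacy is secondary and descriptive, with no hypotheses. Escalation rests on safety review, the maximum tolerated dose is tied elsewhere to the stopping criteria, and central reading starts only after all images have been obtained (Protocol 16.1). The SAP also sets out no dose selection rule that takes these percentages as input. All of this is correct and keeps the point from being more serious. The summaries remain the study's only aggregate statement of efficacy, and Protocol 10.6 gives efficacy a role in the final choice of dose.

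Third, non-completion may be rare. There is one dosing visit, each call has a 3-day window, and Protocol 7.4.4 asks sites to pursue subjects who withdraw or are lost. That is fair, and the rate used here is an assumption. With 12 per cohort, though, a single case is visible in the percentages.

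Fourth, exclusions would be traceable through Table 01.1, Listing 01.2 and Listing 03, and a reader could rebuild the all-dosed figures by hand. This is true, but a reader should not have to reconstruct the main efficacy summary from listings.

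**Conclusion.** The concern holds and should be fixed. On the natural reading of SAP 4.1 and Protocol 10.2, valid image reads are left out of every efficacy table and figure because of an event after imaging has ended.

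One unreplaced exclusion removes 8.3% of a cohort. In the 10-of-12 illustration it moves the reported LVO percentage by about 8 percentage points up (90.9 − 83.3 = 7.6) or 1.5 points down (83.3 − 81.8). No direction of bias is claimed. The chance of at least one such subject in a cohort of 12 is 46% at an assumed 5% non-completion rate, and 31–72% over 3–10%.

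The conclusion rests on follow-up counting as an evaluation period. The size rests on the assumed rate and the illustrative responder count. The primary safety analysis uses the Safety Set and is not affected. If every dosed subject completes, no result changes.

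**What to change.** In SAP 4.1 and Protocol 10.2, define the FAS as all subjects who received NH002 and have at least one centrally read post-injection image, analysed by dose received and regardless of follow-up completion. State that the two change-from-baseline LVEBD endpoints use those FAS subjects who also have a baseline read, which agrees with SAP 5.1.1. A subject read in only one view needs no special set: SAP 5.7 already uses available data without imputation.

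Keep completion as a Per Protocol criterion only. In SAP 4.2, define what completing all study evaluation periods means, including how an unanswered Day 4 or Day 7 call is treated.

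The cost is one or two sentences in each document, plus whatever approval a protocol amendment needs under Protocol 13.1. No new data are required, since the reads are already transferred and listed on the Safety Set. Efficacy figures may move slightly in either direction. If the sponsor does not want to amend the protocol, adding Safety Set versions of the efficacy tables in the SAP would put the excluded reads back into a summary, but the FAS definition would still need the clarification.
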